Subjects who meet all the inclusion/exclusion criteria will be invited to participate in the study. Eligible subjects will be randomized by way of a stratified random sample. The sample frame will be divided into strata based on BMI, sex, and age. Subjects from each stratum will then be randomized to 1 of 4 groups: 1) ADF, 2) aerobic exercise, 3) combination (ADF plus aerobic exercise), or 4) control. **A total of n = 360 subjects (n = 90 per intervention group) will be recruited.** All the subjects will have the right to withdraw from the study at any time.

## 6.0 Study design and procedures

A 24-week randomized, controlled, parallel-arm feeding trial will be implemented to test the effects of ADF and exercise, alone and in combination, on hepatic steatosis/fibrosis, hepatokines, hepatic insulin sensitivity, and other metabolic disease variables. Obese individuals with NAFLD (n = 360) will be randomized to 1 of 4 groups: (1) ADF (fast day: 25% energy intake, feed day: ad libitum fed, no exercise), (2) exercise (ad libitum fed, training 5 days/week), (3) combination (ADF plus exercise), and (4) control (ad libitum fed, no exercise). Changes in hepatic steatosis will be measured by MRS, and hepatic insulin sensitivity will be assessed by OGTT testing and the Matsuda Index. All study activities will be carried out at the Human Nutrition Research Unit (HNRU) located in the Applied Health Sciences Building ([name]).

### Diet and exercise interventions

Group	Diet protocol	Exercise protocol
Combination (n = 45)	Fast day: 25% energy intake Feed day: Ad libitum fed	5 days/week, supervised 60 minutes, Intensity: 85% HRmax
ADF (n = 45)	Fast day: 25% energy intake Feed day: Ad libitum fed	No exercise
Exercise (n = 45)	Every day: Ad libitum fed	5 days/week, supervised 60 minutes, Intensity: 85% HRmax
Control (n = 45)	Every day: Ad libitum fed	No exercise

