We recently performed a pilot study to evaluate the effects of alternate day fasting (ADF) and exercise, alone or combined, on various hepatic parameters in obese adults. ADF consists of a "fast day", in which 25% of energy needs (~500 kcal) are consumed, alternated with a "feed day", in which food is consumed ad libitum. Results from our pilot study show that the combination of ADF plus exercise produced greater reductions (-21 ± 9%) in alanine aminotransferase (ALT; an indirect marker of hepatic steatosis), compared to ADF alone (-13 ± 4%), or exercise alone (-16 ± 7%) after 12 weeks. Greater decreases in insulin resistance, HbA1c, LDL cholesterol, and more pronounced increases in HDL cholesterol, were observed in the combination group versus individual interventions. Data from our pilot trial also suggest that these decreases in insulin resistance by ADF plus exercise may be mediated in part by changes in hepatocyte-derived hormones (fetuin-A and FGF-21) that occur with liver fat reduction. Although these pilot findings are very promising, these data still require confirmation by a larger-scale (n = 360), longer-term (24 week) clinical trial. Accordingly, the specific aims of this study are:

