## 12.0 Statistical considerations

All continuous variables will be examined for distributions and the presence of outliers. Variables that are not normally distributed will be transformed and if normality cannot be achieved, will be analyzed using non-parametric tests. Standardized descriptive statistics including measures of means, median, standard deviations, ranges, and standard errors for continuous variables within each group will be calculated to describe the groups at fixed time points. Differences between groups at baseline will be assessed by a one-way ANOVA. A repeated measures ANOVA will be used to evaluate the effects of diet, exercise, and their interaction (diet x exercise) on dependent variables; a significant interaction will be interpreted with a Bonferroni correction for multiple comparisons. A multivariate analysis that adjusts for the effects of confounding variables (age, sex, race, and baseline hepatic steatosis, hepatic insulin sensitivity, hepatokine profile, body weight, and body composition) will also be performed. Relations between continuous variables will be assessed by Pearson's or Spearman's correlation coefficients as appropriate. Data will be analyzed using SPSS software (SPSS, Chicago, IL).

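### The intervention table in Section 6.0 gives 45 participants per group (180 in total), but Section 5.0 gives 90 per group (360), and nothing in the readable text reconciles them

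*Combined protocol and SAP*

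**What the plan says.** Five places in the combined protocol and SAP (Version 13) bear on the size of the trial.

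- **Section 5.0, Subject enrollment**, sets the recruitment target: "A total of n = 360 subjects (n = 90 per intervention group) will be recruited". It is the only place that gives both a total and a group size of 90.
- **Section 6.0, opening paragraph**: "Obese individuals with NAFLD (n = 360) will be randomized to 1 of 4 groups".
- **Section 1.0, Project Summary/Abstract**, under Methods, makes the same statement with the same total.
- **Section 2.0, Background**, closes by saying of the pilot results that "these data still require confirmation by a larger-scale (n = 360), longer-term (24 week) clinical trial".
- **Section 6.0, Diet and exercise interventions table**, which sets out the diet and exercise regimen of each arm, opens its first row with "Combination (n = 45". The ADF, exercise and control rows each carry the same figure of 45.

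Section 12.0, Statistical considerations, names the analysis ("A repeated measures ANOVA will be used to evaluate the effects of diet, exercise, and their interaction (diet x exercise) on dependent variables"). It gives no sample size calculation, alpha, sidedness, power, effect size, standard deviation or dropout allowance.

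**The concern.** The number per group is a basic design figure, and the table that defines the four arms shows half the number given in Section 5.0. The conflict lies within Section 6.0 itself, because its opening paragraph stands directly above the table.

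Usually a power calculation would show which figure governs. There is none here, so the stated number is the only definition of the trial's size. Someone who takes the group size from the table would plan for 180 participants and later judge recruitment against 180. If about 180 were enrolled, the same document could be cited to show that the trial met its target or that it stopped at half. The two sizes also give different precision for every between-group comparison, and Section 1.0 presents this as the adequately powered confirmation of a pilot.

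**Working it through.** **Inputs from the documents**

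- Number of groups: 4 (Section 5.0: "Subjects from each stratum will then be randomized to 1 of 4 groups").
- Group size in Section 5.0: 90; total 360.
- Group size in the Section 6.0 table: 45 in each of four rows; no total shown.
- MRS scans per participant: 3 (weeks 1, 13 and 24, Section 6.0).

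**Step 1. Reproduce the stated total.** 4 × 90 = 360. This agrees with Sections 1.0, 2.0, 5.0 and the opening of 6.0.

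**Step 2. Total from the table.** 4 × 45 = 180. The gap is 360 − 180 = 180 participants, and 180/360 = 50%. In MRS scans, 3 × 180 = 540 against 3 × 360 = 1,080.

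**Step 3. Look for a reading that reconciles the two.**

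- *360 recruited, 180 allocated.* Ruled out: Sections 1.0 and 6.0 say that the 360 are randomized.
- *45 as completers.* The table carries no such label. Going from 90 to 45 needs dropout of 1 − 45/90 = 50%, a rate stated nowhere. Working upward from 45 with n/(1 − d), assumed dropout of 10%, 20% and 30% gives 50, 57 and 65 per group, well short of 90.
- *90 as a factorial margin (two cells of 45).* The trial would then total 180, which still contradicts 360.
- *A stage, cohort or subset.* None is described.
- *Damaged table or superseded text.* All four rows carry the same intact figure, and the table is operative text, not an amendment log.
- *The 360 ml in Section 7.0.* This is a blood volume and has no bearing.

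**Step 4. Illustrate the statistical consequence.** The documents give none of the inputs, so these are assumptions: two-sided alpha 0.05, 80% power, and a simple comparison of two groups, not the planned repeated measures ANOVA. In SD units, the detectable difference is (1.960 + 0.842) × √(2/n).

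| Assumption | 90 per group | 45 per group |
|---|---|---|
| No dropout | 2.802 × √(2/90) = 0.418 | 2.802 × √(2/45) = 0.591 |
| 10% dropout (n = 81; 40.5) | 0.440 | 0.623 |
| 30% dropout (n = 63; 31.5) | 0.499 | 0.706 |
| No dropout, alpha 0.025 (Bonferroni for the combination group against each single intervention) | 0.460 | 0.650 |

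Fractional group sizes are averages, kept only for the arithmetic. A difference of 0.418 SD, detectable with 80% power at 90 per group, has power Φ(0.418/√(2/45) − 1.960) = 0.508 at 45 per group, about 51%.

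**The case against.** The strongest reply is that this is a slip in a table whose purpose is to list regimens. Section 5.0 is explicit, the paragraph above the table says 360, and no calculation in the documents uses either 45 or 90. On that view a reader would have to overlook two clear statements to be misled, and the matter is editorial.

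This is fair about the likely cause, and the table is indeed the likelier error. It does not remove the contradiction. The planned group size is a figure the trial relies on, and there is no sample size justification against which to check either number.

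Four further points on the other side are partly right:

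- The mentions of 360 are not independent confirmations, since Sections 1.0 and 6.0 carry essentially the same sentence. The case for 360 rests mainly on the explicit target in Section 5.0, so the sponsor should confirm the figure before the text is edited.
- A figure and the content under one heading in Section 6.0 are missing from the extracted text. The claim is therefore limited to the readable text.
- The power figures rest on assumed inputs and a simpler test than the one planned. They illustrate the consequence, and the finding does not depend on them.
- This is an internal inconsistency and not a miscalculation: 4 × 90 does equal 360.

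**Conclusion.** The concern holds, with high confidence. As written, the group size is contradictory by a factor of two: 45 per group (180) in the Section 6.0 table, against 90 per group (360) in Section 5.0 and 360 in three other places. That conclusion uses document figures only and needs no assumption.

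The documents favour 360 but do not prove it. The statistical consequence (0.42 against 0.59 SD detectable, or 80% against about 51% power at 0.42 SD) depends on the assumed alpha, power, zero dropout and two-group comparison. With 10% to 30% dropout the detectable differences become 0.44 to 0.50 SD and 0.62 to 0.71 SD. The point must be fixed, because it concerns a basic design figure and the correction is nearly free.

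**What to change.** The sponsor should confirm the intended number, and the protocol should then show one figure throughout.

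- **If 360 is the target (the better-supported reading):** change the four rows of the Section 6.0 table from 45 to 90, in line with Section 5.0. This costs four table cells, with no change to design, endpoints or analysis and no added participants.
- **If 180 is the target:** correct Sections 1.0, 2.0, 5.0 and the opening of 6.0. This is a text edit only if 180 was already the working target. Otherwise it halves the stated recruitment and should be recorded and justified as a change to the plan.
- **If 45 means something else, such as expected completers:** label it so in the table and state the dropout that it implies.

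In the same revision, a short sample size justification in Section 12.0 (alpha, power, effect size, SD and dropout) would let a reader check whichever number is kept.

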### Diet protocol

**ADF group and combination groups:** These participants will consume 25% of their baseline energy needs on the "fast day" and eat ad libitum at home on alternating "feed days".

**Fast day (week 1-4):** All fast day meals will be provided to subjects during week 0-4. Meals will be prepared in the metabolic kitchen of the HNRU. The diets will be provided as a 3-d rotating menu comprised of typical American foods. Meals will be formulated on the basis of the American Heart Association (AHA) guidelines (30% kcal from fat, 15% kcal from protein, and 55% kcal from carbs). All meals will be consumed outside of the research center. **Fast day (week 5-24):** At week 5, fast day meals will no longer be provided to subjects.

Instead, subjects will meet one-on-one with a dietitian for 60 min to learn how to self-select healthy foods

to stay within the calorie limits on the fast day. **Feed day:** On the feed day, subjects will eat ad libitum at home.

**Exercise group and control groups:** These participants will be asked to maintain their regular eating habits during the trial. They will eat ad libitum at home every day, and will not receive any packaged meals or dietary counseling.

### **Exercise protocol**

[figure not shown]
**Exercise group and combination groups:** Only combination and exercise groups will partake in the exercise training. All training sessions will be conducted at the subject's home. Subjects will participate in a supervised aerobic exercise program 5 times per week, 40-60 min/d, for 24 weeks. Exercise will be performed by watching YouTube aerobic exercise (Zumba) videos at home. The video links will be provided by the study coordinator prior the exercise session. The coordinator conducting the study session on Zoom will have immediate knowledge of the subject's location so that they can relay this information to emergency personnel if needed. During the week 1 sessions, subjects will exercise for 40 minutes at a moderate intensity (65% heart rate max (HRmax)). During the week 2 sessions, subjects will train for 50 minutes at a higher intensity (75% HRmax). For weeks 3-24, subjects will train for 60 minutes at an even higher intensity (85% HRmax). The participants will wear heart rate monitors (Fitbit Alta HR, Boston, MA) during each training session to provide visual feedback of their individualized target heart rate. Fitbit monitors will be distributed to subjects so that they can monitor their heart rate at home. **Compliance with the training:** A research assistant will be present to supervise all the training sessions over Zoom. All sessions will be pre-scheduled with the research assistant so the participant knows when to enter the Zoom meeting to perform the activity. Exercise will be carefully documented through regular online attendance at the training sessions. Subjects will be permitted to choose the day and time slot that works best for them. If a subject misses their session, they will be required to make up for it that same week. Subjects will be permitted to miss 5 sessions total during the 24-week trial.

**ADF group and control groups:** ADF and control subjects will be asked to maintain their regular daily activity habits during the study. They will not participate in the exercise protocol.

**Control group protocol:** Controls will be instructed to maintain their weight throughout the trial, and not to change eating or physical activity habits. Controls will not receive packaged meals or dietary counseling. Controls will visit the research center at the same frequency as the treatment groups (for outcome measurements) to control for investigator-interaction bias between groups. Controls will be offered free weight loss diet counseling (4 sessions) at the conclusion of the study by [name], MS, RD.

**Subject compensation.** Each subject will receive \$500 upon completion of the trial. Compensation will be prorated (please see Initial Review application for details).

## Summary of intervention groups and key outcome measures

## Study activities

Study activities	Study visits (week of study)																								
	Screen	1	2	3	4	5	6	7	8	9	10	11	12	13	14	15	16	17	18	19	20	21	22	23	24
Informed consent	•																								
Screening questionnaire	•																								
Michigan Alcohol Screening test	•																								
Pregnancy test	•	•																							•
Body weight (at home)	•	•	•	•	•	•	•	•	•	•	•	•	•	•	•	•	•	•	•	•	•	•	•	•	•
Blood draw	•	•																•							•
Blood pressure/heart rate		•																•							•
Body composition (BIA)		•																•							•
Waist circumference		•																•							•
Body composition (DXA)		•																•							•
Activity monitor		•																•							•
Hepatic insulin sensitivity (OGTT)		•																•							•
Hepatic steatosis (MRS)		•																•							•
Food record	•	•																•							•
Sleep questionnaires		•																•							•
Time per visit:	1	4	0	0	0	0	0	0	0	0	0	0	0	0	0	0	0	0	0	0	0	0	0	0	4

**Body weight, blood pressure, heart rate:** Body weight measurements will be taken weekly with subjects wearing light clothing and without shoes using a balance beam scale at home. Digital scales will be provided to each subject. Height will be assessed using a wall-mounted stadiometer at week 1. BMI will be assessed as kg/m^2. Blood pressure and heart rate will be assessed at week 1, 13, 24.

**Body composition:** Dual energy X-ray absorptiometry (DXA) will be performed on all subjects at week 1, 13, and 24 (iDXA, GE Inc) to assess fat mass, fat free mass, and visceral fat mass. Percentage body fat will be assessed in triplicate using a tetra-polar bioelectrical impedance analyzer each week (Omron HBF-500; Omron Health Care, Bannockburn, IL). Waist circumference will be measured weekly.

**Hepatic steatosis by magnetic resonance spectroscopy (MRS):** MR scans will be performed at the Center for Magnetic Resonance Research (CMRR). MR images and spectrum will be acquired using a 3.0 T MR scanner. MR examinations will be performed by experienced MR technologists. Subjects will arrive at the CMRR in the morning following an overnight (8 h) fast. Total hepatic triglyceride content will be assessed at week 1, 13 and 24 by H MRS. A body array MRI coil will be affixed to each subject's back and aligned with the subject's spine and shoulders for accurate repositioning of repeat scans. Each subject will be positioned face down and head first in the scanner on a memory foam mattress to minimize respiratory motion. An 8 cm^3 voxel is positioned within the right posterior lobe of the subject's liver with guidance from the high-resolution localization images. Manual shimming will be performed to a line width of ~40Hz to ensure high quality spectra. MR spectra with and without water suppression will be acquired with a single-voxel PRESS acquisition with a long repetition time (TR=5000ms), and a short echo time (TE=30ms) to limit the effects of magnetic relaxation. The acquisition will be obtained with 32 averages to obtain sufficient signal, and the data will be Fourier-Transformed, filtered, baseline corrected, and phased. Areas of resonances from protons of water and methylene groups in fatty acid chains of the hepatic triglyceride will be evaluated with a line-fit procedure and commercial software (NUTS-ACORNNMR, CA).

**Blood sampling:** Twelve-hour fasting blood samples will be collected at week 1, 13, and 24 consecutive feed and fast days (20 ml at each time point). All blood draws will be performed at the HNRU by [name]. Blood will be centrifuged for 15 min at 520 x g and 4°C to separate plasma from red cells, and will be stored at -80°C at the HNRU. Specimens will be labeled with the subject ID and study week, and will be stored until the study is completed. After the study is over, all specimens will be destroyed.

**Hepatic insulin sensitivity by OGTT and Matsuda Index:** Hepatic insulin sensitivity will be assessed at week 1, 13 and 24 by the oral glucose tolerance test (OGTT) and Matsuda Composite Index. For this procedure, subjects will arrive at the research center in the morning after a 12-h fast. They will have their blood drawn (20 ml), and then be given a 75 g dose of glucose (Thermo Scientific Glucose Tolerance Test Beverage, Waltham, MA). Four blood samples (20 ml each) will be taken 30, 60, 90, and 120 min after the glucose dose for the measurement of glucose and insulin. Hepatic insulin sensitivity will be calculated as Matsuda's Insulin sensitivity index (ISI) = [10000/(fasting glucose x fasting insulin x mean glucose during OGTT x mean insulin during OGTT)1/2].

**Activity monitor:** All subjects will be instructed to maintain their regular daily activity habits (i.e not join a gym or participate in other exercise classes). Alterations in physical activity habits will be quantified by an activity monitor (Fitbit Alta HR, Boston, MA) that will be worn on the wrist for 7 days at week 1,13, and 24.

**Food record:** Dietary intake will be assessed in all groups by a 7-day food record at week 1, 13 and 24. Subjects will be given detailed guidelines on how to complete the records by the Dietician at baseline. Dietary intake data will be assessed by Nutritionist Pro software (Axxya, TX).

**Michigan Alcohol Screening test:** Alcohol consumption will be assessed by the Michigan Alcohol Screening Test at the screening appointment.

**Metabolic disease risk factors:** Plasma metabolic disease risk factors will be assessed at baseline week 1, 13, and 24. Plasma total cholesterol, LDL cholesterol, HDL cholesterol, and triglyceride concentrations will be measured in duplicate using enzymatic kits, standardized reagents, and standards (Biovision Inc, Mountainview, CA) and analyzed using a microplate reader (iMark Microplate Reader; Bio-Rad Laboratories Inc, Richmond, CA). HbA1c will be assessed by ELISA (Mybiosource, San Diego, CA). Fasting plasma glucose concentrations will be measured with a hexokinase reagent kit in duplicate (A-agent glucose test, Abbott, South Pasadena, CA). Fasting insulin will be measured as total immunoreactive insulin (Coat-A-Count Insulin, Los Angeles, CA). Insulin resistance (IR) will be calculated by the HOMA (Homeostasis Model Assessment) method:  $[HOMA-IR = \text{Fasting insulin } (\mu\text{U/ml}) \times \text{Fasting glucose } (\text{mg/dL}) / 405]$ .

**Proteomics and metabolomics:** Plasma-derived proteomic and metabolomic outcomes will be measured using immunoassay and mass spectrometry, as described previously.

**Hepatokine plasma levels:** Plasma hepatokines will be measured at week 1, 13, and 24. Commercially available ELISA kits will be used to measure concentrations of Fetuin-A, fetuin-B, FGF-21, SHBG, and RBP4, (R&D Systems, Minneapolis), and adiponectin and selenoprotein P (Mybiosource, San Diego, CA). All samples will be assessed in duplicate.

**Inflammation:** Inflammatory markers will be measured at week 1, 13, and 24. C-reactive protein (CRP) will be measured in duplicate using Immulite 1000 High Sensitivity CRP kits (Diagnostic Products Corporation, Los Angeles, CA). Adiponectin, leptin, TNF- $\alpha$ , and IL-6 will be measured using ELISA (R&D Systems, Minneapolis, MN).

**Sleep questionnaires:** Sleep quality and duration will be measured by validated questionnaires at week 1, 13, and 24. The severity of insomnia in the past week will be measured by the Insomnia severity index (ISI), which is a 7-item questionnaire. Each item is rated by a 5-point Likert scale (where 0 indicates no problem, and 4 indicates a very severe problem) yielding a total score of 0-28. The total score for the ISI is interpreted as follows: no clinically significant insomnia (0-7), sub-threshold insomnia (8-14), moderate severity insomnia (15-21), and severe insomnia (22-28). Sleep quality, timing and duration will be measured by the Pittsburgh Sleep Quality Index (PSQI). This 19-item self-report questionnaire measures total sleep quality in the past month, yielding a total score of 0-21. A PSQI total score  $>5$  indicates poor sleep quality. The questionnaire also asks for usual bedtime, usual wake time, and hours of actual obtained sleep. Risk of obstructive sleep apnea will be estimated using the Berlin Questionnaire at baseline.

